2.2 DETAILED DESCRIPTION OF STUDY DESIGN

Study Population: The study population will consist of injured patients at risk of hemorrhage being transported via air medical services from the scene of injury or from referring hospital to a definitive care trauma center participating in the PPOWER pilot trial. Patients will be enrolled in the prehospital setting prior to trauma center arrival with continuation of LTLR-WB resuscitation or standard of care resuscitation during the in-hospital acute resuscitation phase of the study.

Study Population Rationale: The most appropriate patient population who would benefit most from early, prehospital initiation of LTLR-WB are those with potentially survivable injuries, at risk of the detrimental complications attributable to hemorrhagic shock, using criteria which can be widely generalizable in the real-world prehospital setting. In the prehospital phase of treatment, complete characterization of injuries and injury severity is not possible. We have chosen inclusion and exclusion criteria based upon preliminary data obtained from the PAMPer study, a recently closed pragmatic prehospital trial at the University of Pittsburgh.⁴⁰ The incidence of arrival shock (87%) and coagulopathy (41%), the need for large volume transfusion (36%) and the development of multiple organ failure (25%) and overall mortality (30%) utilizing the proposed inclusion and exclusion criteria, with appropriate modifications, will provide the most appropriate patient population to demonstrate the benefits of LTLR-WB resuscitation.

Group O whole blood represents a precious blood banking resource. There exists an even further limited supply of Rh negative, group O whole blood (6.6% of blood supply overall). Due to this supply limitation, the only feasible and sustainable approach for whole blood resuscitation is to utilize Rh positive group O whole blood, which is significantly more common (37.4% of blood supply overall).

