2.3 STUDY INTERVENTION

The study intervention will be the initiation of prehospital through in-hospital transfusion of LTLR-WB in patients meeting all inclusion and no exclusion criteria. Whole blood units will be obtained from a local FDA licensed blood center (LifeSource dba Central Blood Bank; Registration number: 2571073; License number: 1025).

Up to two units of LTLR-WB (O+) will be initiated in the prehospital phase of the study with an additional 6 units of LTLR-WB (O+) available during the in-hospital phase of the trial if indicated.

Study Intervention Rationale: To provide the earliest and most robust intervention with appropriate concern for blood banking resource utilization, a prehospital and in-hospital phase intervention will be utilized. As whole blood resuscitation is most pertinent to patients with acute hemorrhage, we have limited the in-hospital acute resuscitation phase time period and the additional 6 units of LTLR-WB to 4 hours post-admission. This acute phase resuscitation period definition is based upon unpublished data from the recently completed PAMPer study at our institution.⁴⁰ Over 79% of the blood products transfused in the first 24 hours occurred in the first 4 hours following admission.

Whole Blood Intervention: Blood from male only, group O+ donors will be collected using the FDA approved Terumo Imuflex® WB-SP blood bag system. With this collection system, whole

blood passes through a platelet sparing inline leukoreduction filter into a bag containing citrate phosphate dextrose solution. Male only whole blood donors will be used in order to mitigate the risk of transfusion related acute lung injury (TRALI; estimated incidence ≈1:12,000). Whole blood collected with this system can be kept as such for up to 21 days when stored between 1-6°C. Per blood bank protocol, the anti-A and anti-B antibody titers in each unit will be tested on a sample from every donor using an immediate spin saline tube method without incubation; only units where the titer of both anti-A and anti-B are <100 will be issued for the study and subsequent transfusion. All other required transmissible disease testing will also be performed on these LTLR-WB units before they are released, as per blood bank standard practice. The LTLR-WB units will have affixed on them the standardized Whole Blood product label thereby making them easily distinguishable from the other non-WB units in inventory.

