2.4 INTERVENTIONAL ARM

Prehospital Phase Interventional Arm: Two units of LTLR-WB (O+) will be stored at each helicopter base in temperature regulated blood bank approved refrigerators for up to 14 days, which is the period within which cold stored platelets are thought to retain maximal function. Two units of LTLR-WB will be transported on all air medical flights with prehospital staff in blood banking approved and verified coolers. The temperature of the blood will be monitored throughout transit and storage in accordance with standard blood banking and Stat MedEvac procedures. Following 14 days without use, LTLR-WB will be replaced with new LTLR-WB units and the old products will be returned to the blood bank for recycling into PRBCs.. During transport, storage and during all flights standard STAT MEDEVAC protocols for storing and carrying blood products at the base and on the helicopters will be followed. While at the bases the blood units are stored in a dedicated blood refrigerator and moved to cooler for transport only when the aircraft is launched. The blood is packaged in the coolers with a thermometer for temperature maintenance to assure that they are maintained at 2-5 degrees Celsius at all times. The Clinical Protocol that is currently followed and will be followed for all blood products in the study can be found in Appendix 1. Our FDA approved blood bank will follow all regulations required by the FDA for safe blood and blood component transfusion. On day 15, after ensuring the WB unit had remained in temperature compliance and is otherwise eligible for recycling according to 21 CFR 640.2(c), the WB unit will be recycled into a PRBC unit following the standard operating procedures at the Centralized Transfusion Service in Pittsburgh.

Patients who meet all inclusion and no exclusion criteria at the scene, at a referral hospital or during transport and are randomized to the interventional arm will receive up to 2 units of LTLR-WB (O+) en-route to a PPOWER participating trauma center based upon hemodynamic status using identical criteria as the Prehospital Standard of Care arm. If the intervention is completed during transport, standard operating procedures for the prehospital setting will be employed by the prehospital providers during the remaining flight. (Appendix 7)

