6.4.5 Reportable Adverse Events

Assessing and Reporting Adverse Events (AEs): Enrolled subjects will be monitored for adverse events throughout the first 48 hours after hospital admission. Reporting forms will be submitted to the DSMB and IRB. Potential adverse events occurring within the first 48 hours after admission will be reviewed as to treatment arm and further classified by: a) Severity (life-threatening, serious, non-serious); b) Expected vs. Unexpected; and c) Related, Possibly Related, Probably Not Related, or Definitely Not Related. For serious adverse events that are related or possibly related to the study or intervention, the coordinating center will notify the IRB and the DSMB as well as additional appropriate regulatory agencies and sponsor promptly. The coordinating center will tabulate and report compliance, data quality, and non-serious adverse events on a regular basis.

Expected adverse events are commonly observed in patients who are at risk of hemorrhage following traumatic injury and may or may not be attributable to the LTLR-WB. Clinical diagnoses of pneumonia, sepsis, cerebral bleeding, stroke, seizures, surgical interventions, complications due to specific injuries as well as other major medical or surgical complications are commonly

observed in these patients. They will be recorded as noted in the hospital discharge summary as complications and will not be reported as adverse events.

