6.4.6 Adverse Events Reporting Timeline

Organization	Fatal/Life Threatening SUSAR	Non-fatal, non-life threatening SUSAR	SAE (expected and related)	UP (not involving risk)	UPIRTSO
IRB	24 hours	10 working days	No requirement	No reporting**	10 working days
FDA	7 calendar days	15 calendar days	No requirement	No requirement	14 days*
NHLBI	7 calendar days	7 calendar days	No requirement	No requirement	14 days*
Medical Monitor	24 hours	7 calendar days	No reporting	No reporting	14 days*
DSMB	24 hours	7 calendar days	At next meeting (every 6 months)	At next meeting (every 6 months)	14 days*

A table summarizing reporting timelines is provided below:

*Reporting occurs only after an IRB determination of UPIRTSO has been received

**No direct reporting is required; events are documented on a log that can be reviewed upon request

Prehospital Transfusion Adverse Events/Look Back Standard Operating Procedure (SOP):

a. Transfusion rate will be compatible with the patient's condition. The patient will be monitored closely during the entire transfusion. The documented start and stop times are directly related to the actual transfusion of the component. Study coordinators will assume responsibility of additional vital signs and completion of the whole blood

b. The patient medical record shall include the following:

- 1. Name of the components transfused
- 2. Donation identification number
- **3.** Date and time of transfusion (Start and Stop time)
- 4. Pre and post transfusion vital signs
- **5.** The volume or **#** of units transfused
- 6. The transfusionist's name (paramedic)
- 7. Documentation of related adverse events

c. Procedure for transfusion reactions:

This is modified from UPMC policy for Blood Transfusions to be applicable for this study.

1. Careful observation throughout the transfusion allows for early detection of adverse reactions and optimal treatment, if necessary. All reactions should be handled initially as possible hemolytic reactions and the transfusion must be stopped. Any adverse events associated with the transfusion of blood or blood components should be documented in the patient's Medical Record and reported to the blood bank/ transfusion service. Prehospital providers initiating transfusion of blood products will monitor vitals

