throughout transport. If clinical concern for a transfusion reaction occurs, the transfusion will be stopped, and supportive care will continue. The concern for a transfusion reaction will then be communicated to the trauma center staff.

2. The most common clinical events accompanying or announcing transfusion reactions are, in order of decreasing frequency:

a. Fever, with or without chills

b. Skin symptoms, hives and/or itching or rash

c. Chest pain

d. Hypotension

e. Nausea

f. Flushing

g. Respiratory Distress (wheezing, coughing or dyspnea)

h. Bleeding at infusion site

i. Hemoglobinuria

j. Circulatory overload

k. Anaphylaxis

3. If an adverse reaction is suspected, the procedure below will be followed:

a. Stop the transfusion

b. Maintain IV access with Normal Saline and change the tubing.

c. Notify the patient's physician upon arrival to the ED and initiate immediate treatment as ordered.

4. For all other blood products involved in a reaction, all blood products shall be stopped and a transfusion reaction investigation shall be initiated per standard blood bank guidelines

5. Notify the Blood Bank of the suspected transfusion reaction.

6. Collect a sample drawn from the patient as soon after the reaction was detected. Send a 6 mls pink top tube, labeled with a new Blood Bank armband to the Blood Bank along with the unused blood, blood bag with attached hard back copy of the transfusion tag, the IV tubing used and the top 2 copies of the Transfusion Reaction Investigation 3 part form. The back copy of the Transfusion Reaction Investigation form should remain in the patient's chart as the initial report. A post transfusion reaction Urinalysis with Microscopic may also be ordered by the patient's physician.

7. The Blood Bank will complete the Transfusion Reaction initial report and notify the caregiver of the critical results. Pathology will evaluate the patient's reactions, Blood Bank's initial report, culture when indicated, and report will be documented in the patient's medical record. Consultation between the Medical Director of the Transfusion Service, the patient's physician and Risk Management is required when a fatal hemolytic transfusion reaction occurs. Further evaluation and FDA notification may be indicated. The participating centers Transfusion Service is responsible for peer review and blood utilization practice.

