9. Initials of person doing inspection.

b. Ensure refrigerator is clean and in working order.

3. Visual Inspection: Check appearance for contamination, clots,

discoloration, etc. List as satisfactory or unsatisfactory. 4. Initials: Your

initials.

- 5. Comments: Insert flight number and patient name if blood product was transfused.
- 7. Packing blood products for a mission
 - a. Blood products are to be taken on every mission.
 - b. Each unit should be in the plastic blood product bags
 - c. Place in the insulated cooler with commercial ice packs or ice and an appropriate thermometer. The units should be "sandwiched" between the ice using appropriate barriers to prevent the units from coming in direct contact with the ice.
 - d. If blood is not transfused, return it to the blood product refrigerator upon returning to base. Fill out remaining Columns 6-10 of Blood Tracking Log
- 8. Administration of blood products is to be carried out in strict accordance with STAT MedEvac Critical Care Protocols.
- 9. Documentation of transfusion
 - a. When a unit is transfused during a mission make sure the appropriate information is relayed to the receiving facility including type and unit number.
 - b. Fill out appropriate blood bank forms for transfused products per Central Blood Bank / American Red Cross instructions.
 - c. Upon return to the base, fill out the Blood Tracking Log for Columns 6-10 as
 - instructed.
- 10. Replacement of transfused blood products
 - a. Notify appropriate blood bank that you have transfused blood and specify the number of replacements needed.
 - i. Notify STAT Com and the Medical Director on call of any delay in receiving replacement units of blood and document the delay via special report.
- 11. Transfusion Complications
 - a. Notify the receiving facility of the patient's signs and symptoms immediately upon arrival.
 - b. Upon returning to base, an Adverse Reaction special report should be completed.

- 11. Blood refrigerator alarms
 - a. Monthly Check- High and low temperature alarms to be checked on the first of every month.
 - i. Remove blood from refrigerator and place on ice in cooler.
 - ii. Remove probe from glycerol solution and place the probe on ice. Temperature of probe will register below 1_c C within several minutes to activate alarm.
 - iii. The designated operator should call to advise of the Alarm. Activate the silence button on the blood product storage refrigerator after receiving phone call.

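### The adverse-event window in 6.4.5 opens at admission, so non-hemolytic reactions that begin in flight have no stated route into the trial's AE classification or by-arm tabulation

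*Combined protocol and SAP*

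**What the plan says.** Section 6.4.5 sets the AE clock at admission twice. The monitoring rule is: "Enrolled subjects will be monitored for adverse events throughout the first 48 hours after hospital admission". The review rule is: "Potential adverse events occurring within the first 48 hours after admission will be reviewed as to treatment arm"; those same events are then classified by severity, expectedness and relatedness.

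Study treatment starts earlier. Section 2.2 states: "Patients will be enrolled in the prehospital setting prior to trauma center arrival". Section 2.3 adds: "Up to two units of LTLR-WB (O+) will be initiated in the prehospital phase of the study". Under 2.5, control patients may receive red cells and crystalloid over the same period.

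Section 6.4.6 contains a separate procedure for prehospital transfusion reactions. It requires close monitoring, an entry in the medical record and a report to the blood bank. On arrival, "The concern for a transfusion reaction will then be communicated to the trauma center staff". Appendix 1 adds a report by the flight crew: "Upon returning to base, an Adverse Reaction special report should be completed".

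**The concern.** The trial asks whether whole blood started before arrival is safe and effective, and prehospital initiation is what sections 1.4 and 2.8 present as new. The arms first differ in flight. An AE window that opens at admission leaves that phase out of the only step in which the plan describes grading and attributing adverse events and reviewing them by arm. Section 6.1 lists febrile, allergic and anaphylactoid reactions, TRALI and TACO among the transfusion risks, and any of these could begin before landing.

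Two things are at stake: the by-arm AE figures given to the DSMB, and the safety estimates that the pilot is meant to hand on to the large multicenter trial. There is also a consistency problem. One coordinator could follow 6.4.5 and leave an in-flight reaction off the AE form, while another could follow the spirit of 6.4.6 and enter it. The trial is open label and assigned by helicopter base and month, so nothing guarantees that such differences would be the same in the two arms.

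**Working it through.** No arithmetic applies; the plan states no figure on this point. The check is to order the events in time and then follow an in-flight reaction along every route the documents offer.

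**Order of events.** Enrollment, then the first prehospital product, then admission, then 48 hours after admission. Section 6.4.5 covers only the last interval. No other section moves its start earlier.

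**Which events fall outside.** Onset decides. A reaction to an in-flight unit that first appears after arrival is inside the window. A reaction with onset before admission is outside it.

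**Routes for a reaction with onset before admission.**

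| Route | Scope | Where it leads |
|---|---|---|
| 6.4.6 prehospital procedure | Any suspected reaction, any blood product | Medical record, blood bank, treating physician, trauma center staff; no study AE form or tabulation by arm is named |
| Appendix 1 special report | Transfusion complications | Completed at the base; no study recipient is named |
| 6.5.1 data collection | Air medical care reports | Reviewed for study data, but the listed prehospital items do not include transfusion reactions |
| 2.8 secondary outcome | Acute hemolytic reactions only | Compared by arm, from randomization |
| 2.8 and 2.9 mortality | Deaths of enrolled patients | Counted by arm under intention to treat, although 2.8 times deaths from admission |
| 6.4.2 and the 6.4.6 reporting table | Unexpected, related serious events | Expedited reporting with no admission start, but only after expectedness and relatedness have been judged |
| 6.4.2 DSMB review | AE rates by arm, about every 6 months | No start time is given; the rates depend on what has been collected |
| Appendix 8 tables | Hemolytic reactions (Table 4), unanticipated events (Table 5) | No row for other transfusion reactions |

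**A worked case.** Suppose an allergic reaction begins during the first prehospital unit and resolves before landing. Under 6.4.6 it is documented, reported to the blood bank and handed over. It is not hemolytic, so the secondary outcome does not capture it. If it is judged expected or not serious, expedited reporting does not apply. Under 6.4.5 its onset precedes admission, so the classification and by-arm review do not reach it. The same holds for a control patient who reacts to prehospital red cells.

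**The case against.** The strongest reply is that the plan does look after in-flight reactions. The 6.4.6 procedure is part of the protocol and adapted for the study. Research staff are present on arrival (2.6), coordinators verify air medical arrivals (6.5.2), and flight records are reviewed (6.5.1). Section 6.1 names hemolysis as the primary whole-blood risk, and that outcome is compared by arm from randomization. Expedited reporting and DSMB review are not tied to admission. One sentence in 6.4.6 about study coordinators breaks off in the text and may name a study form.

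Most of this stands, and it rules out several stronger readings that a reader might infer:

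- *In-flight reactions go unrecorded.* They do not; detection and documentation are required.
- *All reactions to in-flight units are lost.* Only those with onset before admission fall outside the window.
- *A death in flight is invisible to the comparison.* Deaths of enrolled patients count in the intention-to-treat mortality analysis.
- *The gap favors whole blood.* Controls may receive prehospital red cells under the same rules, so the gap applies to both arms, and the documents do not show the direction of any bias.
- *A quarter of exposure is unmonitored.* Two of the maximum eight units is 2/8 = 25%, but that is a share of units, not of reactions missed. The same applies to the observation that patients needing no in-hospital blood have 100% of theirs started before admission.

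The reply does not supply a rule that brings a non-hemolytic reaction with pre-admission onset into the AE classification. Staff who are present and records that are reviewed make such a rule easy to follow, but they do not replace it. Nothing can be inferred from the broken sentence in either direction.

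**Conclusion.** The point holds in a limited form. Sections 6.4.5 and 6.4.6 do not join up: the first classifies and compares only events after admission, and the second documents earlier reactions without saying that they enter the trial's AE forms, classification or tabulation by arm. The events affected are non-hemolytic, non-fatal reactions with onset before admission, in either arm. Those that are serious, unexpected and related still have an expedited route.

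The number of such events cannot be estimated, because the documents give neither the time from first unit to admission nor a rate of reactions in flight. The primary outcome, 28-day mortality, is not affected.

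The conclusion assumes that 6.4.5 is followed as written and that the incomplete sentence in 6.4.6 does not already route these events to a study AE form. If it does, the remaining task is only to align the window in 6.4.5. The change should be made, since it bears on the trial's own safety question and costs almost nothing.

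**What to change.** In 6.4.5, start both AE monitoring and the by-arm review at enrollment, or at the start of the first prehospital blood product if that is earlier, and keep the end at 48 hours after admission, in both arms. The alternative start is needed because 5.1 allows eligible patients to be enrolled by research staff after they reach the emergency department.

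In 6.4.6, state that reactions documented under the prehospital procedure, including the base's special report and the blood bank's reaction form, are sent to the coordinating center and entered on the AE form with a prehospital or in-hospital flag. Carry that flag into the AE tables given to the DSMB.

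The cost is about two sentences of text, one form field and some extra data entry. Flight care reports are already reviewed for study data; routing the base special report would be a new step. Clinical management does not change.

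### Sections 6.4.5 and 6.4.6 set different notice rules for an expected, related SAE, and the 6.4.5 exemption drops listed complications from AE reporting even when they are judged related

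*Combined protocol and SAP*

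**What the plan says.** Section 6.4.5 reviews potential adverse events in the first 48 hours after admission by arm. It classifies them on three separate axes: severity, expectedness and relatedness. It then sets a notice rule, whose scope is stated as "For serious adverse events that are related or possibly related to the study or intervention". The action required for every event within that scope is that "the coordinating center will notify the IRB and the DSMB as well as additional appropriate regulatory agencies and sponsor promptly". No number of days is given, and nothing restricts the rule to unexpected events.

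The next paragraph of 6.4.5 turns to expected events, which it says "may or may not be attributable to the LTLR-WB". Its list begins "Clinical diagnoses of pneumonia, sepsis, cerebral bleeding, stroke, seizures" and ends with a catch-all for other major complications. Of these events it says: "They will be recorded as noted in the hospital discharge summary as complications and will not be reported as adverse events".

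The table in 6.4.6 has its own column for SAEs that are both expected and related. In that column the IRB, FDA and NHLBI cells read "No requirement", the Medical Monitor cell says there is no reporting, and the DSMB cell reads "At next meeting (every 6 months".

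Section 6.4.2 limits immediate IRB reports to fatal or life-threatening events that are unexpected and at least possibly related. It also has the outcomes of related or possibly related SAEs go regularly to the IRB, DSMB and sponsor, promises a yearly SAE summary to the IRB, and anticipates that the DSMB will compare adverse event rates by arm every 6 months.

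**The concern.** The same serious event, already judged related to the transfusion, is to be notified promptly under one section and may wait for the next DSMB meeting under the other. If it is on the list of complications, it is not reported as an adverse event at all. No sentence says which text governs. Patients are enrolled under exception from informed consent, and Appendix 4 counts independent data monitoring among the protections that this requires. Late or missing notice of a serious, related event weakens that protection. The exemption can also make the by-arm adverse event rates incomplete for the events most relevant to the product's safety.

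**Working it through.** The plan states no figure on this point, so the check is mainly a comparison of texts. Each class below is serious and expected.

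| Class | 6.4.5, prompt-notice sentence | 6.4.6 table | 6.4.5 exemption |
|---|---|---|---|
| Related, not a listed complication | IRB and DSMB promptly | IRB none required; DSMB at next meeting | Does not apply |
| Possibly related, not listed | IRB and DSMB promptly | No column | Does not apply |
| Related, listed (e.g. sepsis) | IRB and DSMB promptly | IRB none required; DSMB at next meeting | Not reported as an AE |
| Possibly related, listed | IRB and DSMB promptly | No column | Not reported as an AE |

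**Can 6.4.5 be read as covering only unexpected SAEs?** Not from its wording. The sentence before it makes expectedness a separate axis, and 6.4.2 writes that limit out where it is wanted.

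**Can the table be read as defining prompt notice?** No. Its IRB cell for this class gives no time, and a wait of up to 6 months for the DSMB is not prompt.

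**Does the exemption reach related events?** Yes. The paragraph accepts that expected events may be attributable to the product and makes no exception for those that are. Section 6.1 names bacterial sepsis as a transfusion complication, and 6.4.5 lists sepsis as an expected event, so the overlap is real.

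**Does the by-arm count change?** Not through the difference between 6.4.5 and the table. That difference is one of timing: an event brought to a 6-monthly meeting is available for the 6-monthly comparison. Only the exemption can remove an event from the adverse event rates. Under section 2.8, pneumonia, bloodstream infection, ARDS and acute hemolytic reactions are compared by arm as secondary outcomes. Stroke, seizures and cerebral bleeding have no such route. Interim analysis item 5 and Appendix 8, Table 5 do not settle the matter: both refer to unanticipated events without defining them, and Appendix 8 has no general AE table.

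**How much accrual fits between two meetings?** Section 2.9 gives 112 patients, a 2.5-year (30-month) enrolment period, and 61 earlier comparable enrolments in 12 months. Even accrual, 1:1 arms and 6-monthly meetings are assumed.

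- Planned rate: 112 / 30 = 3.73 per month; × 6 = 22.4 patients; 22.4 / 112 = 20%; half, about 11, in the LTLR-WB arm.
- Cited rate: 61 / 12 × 6 = 30.5 patients; 30.5 / 112 = 27%; half, about 15, in the LTLR-WB arm.
- For an event at a random time in the cycle the mean wait is 3 months, which halves the totals to about 11 to 15 patients.

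**The case against.** The best defence is that the texts can be reconciled. A cell that sets no requirement is not a ban, so prompt IRB notice is compatible with it. Telling the DSMB promptly and listing the event again at the next meeting satisfies both sections. That stands: following 6.4.5 does not breach 6.4.6. A reader might infer that the rules are mutually exclusive, or that the IRB must not be told, but the documents do not say so. The shortfall runs one way only, for staff who work from the table alone.

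A reader might also take a possibly related sepsis as caught by all three rules. It is not. Section 6.4.5 grades related and possibly related separately, and the table column covers only related events. For possibly related events the table has a gap, not a conflict.

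Nor does 6.4.2 clearly contradict the table. Regular reporting of outcomes to the IRB can be met by the yearly summary promised there. The limits to unexpected events in 6.4.2 suggest that the table may be the intended rule and the prompt-notice sentence the loosely worded one. That is a fair guess at intent, but the text does not say it.

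There are real safeguards. The investigator reviews safety data as they arise (6.4.4), the DSMB chair regularly receives AE and SAE reports (6.4.3), and suspected reactions get a blood bank work-up (6.4.6). Appendix 2 allows emergency meetings and leaves SAE procedures and meeting frequency to the first DSMB meeting. Section 6.1 reports no transfusion reactions in over 200 earlier recipients. These lower the practical risk, but none says which rule applies or limits the exemption.

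Finally, the exemption might be a prior step that sets aside ordinary trauma complications before any rule applies. Even so, it would set aside those judged related.

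**Conclusion.** The point holds as a defect in safety reporting. For an expected, related SAE, the 6.4.6 table permits later DSMB notice than 6.4.5 promises and asks for no IRB notice. For an expected, possibly related SAE, the table is silent. The exemption keeps listed and other major complications from being reported as adverse events even when judged related, and so can remove them from the by-arm rates. The secondary outcomes offset this only in part.

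The figure of 22 to 30 patients is an upper bound on enrolment between meetings, under the assumptions of even accrual and 6-monthly meetings. A reader might take it as a number of patients harmed or put at risk. The documents do not support that, because no event rate is given or assumed and the chair's regular reports could bring the event to light sooner. The 28-day mortality analysis and the sample size are untouched. The change is still worth making: under exception from informed consent the route for a serious, related event should be unambiguous, and the correction is small.

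**What to change.** 1. Limit the exemption in 6.4.5: listed complications are not reported as adverse events *unless serious and judged related or possibly related to a transfusion given under the protocol in either arm*. Naming both arms keeps the criterion symmetric, since control patients also receive blood products.
2. Widen the table column in 6.4.6 to *SAE (expected, related or possibly related)*. Make its DSMB and IRB cells agree with the prompt-notice commitment, in stated days. The table's existing 7 calendar days for the DSMB and 10 working days for the IRB would serve.
3. If the sponsor intends the 6-monthly route, restrict the prompt-notice sentence in 6.4.5 to unexpected SAEs instead. The exemption should still be limited as in item 1.

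The Medical Monitor, FDA and NHLBI cells need not change. Applying the table's 24-hour times to expected events would be a policy choice and is not needed to remove the inconsistency.

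The cost is a sentence or two in 6.4.5, one column heading and two cells, with no new visits or tests. There will be some added reports. Relatedness would have to be judged for listed complications, and because that judgement is open label, events in the LTLR-WB arm may be called related more readily.
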